9.4 SUPPORTIVE CARE

Clinical judgment may be used to alter the following guidelines without being a protocol violation:

During all phases of therapy

Anti-emetics may be used.

Filgrastim (G-CSF) may be used according to institutional practice and/or ASCO guidelines.

Patients developing dermatologic toxicities while receiving cetuximab should be monitored for the development of inflammatory or infectious sequelae, and appropriate treatment of these symptoms initiated. Dose modifications of any future cetuximab infusions should be instituted in case of severe (grade 3) acneform rash/desquamation (section 9.3.1). Treatment with topical and/or oral antibiotics should be considered; topical corticosteroids are not recommended. If a patient experiences severe acneform rash/ desquamation, cetuximab treatment adjustments should be made according to the table above (section 9.3.1). In patients with mild and moderate skin toxicity, treatment should continue without dose modification.

During the second phase of therapy (while patients are receiving irinotecan)

Anti-convulsants: Enzyme-inducing anti-convulsants (phenytoin, phenobarbital, carbamazepine) should be avoided. Patients who require an anti-convulsant should be treated with a non-enzyme inducing anti-convulsant for a minimum of 4 half-lives of the anti-convulsant agent prior to starting treatment with irinotecan. Documentation of this should be included on the Concomitant Medication form in the Case Report Forms.

Diarrhea: Prophylaxis with an oral cephalosporin (such as cefixime 8 mg/kg/day, maximum 400 mg/day) may be used [J Clin Oncol 2006; 24:563-570]. For early onset diarrhea (during irinotecan infusion or shortly after the infusion), consider atropine (0.01 mg/kg, maximum 0.4 mg) and octreotide. For later onset diarrhea, consider prompt use of loperamide, and consider octreotide if that does not adequately control diarrhea. Suggested loperamide (1 caplet = 2 mg, 1 teaspoon = 5 ml = 1 mg) dosing follows:

- Patients > 43 kg: Take 4 teaspoons or 2 caplets after the 1st loose bowel movement followed by 2 teaspoons or 1 caplet every 2 hours. During the night the patient may take 2 caplets every 4 hours rather than 1 caplet every 2 hours.
- Patients > 30 to 43 kg: Take 2 teaspoons or 1 caplet after the 1st loose bowel movement followed by 1 teaspoon or ½ caplet every 2 hours. During the night the patient may take 1 caplet every 4 hours rather than ½ caplet every 2 hours.

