12.0 CRITERIA FOR THERAPEUTIC RESPONSE/OUTCOME ASSESSMENT

The study's primary aim is to increase the proportion of patients achieving 1-year progression-free survival. Progression-free is defined as lack of unequivocal tumor progression or treatmentassociated death. Unequivocal tumor progression will be determined (usually via brain MRI) by a POETIC institutional radiologist. If radiological studies suggest possible, but not unequivocal progression, the patient may remain on study until unequivocal progression has been determined. In select cases biopsy may be necessary to distinguish tumor recurrence from radiation effect.

In this study, we will compare the product of 2-dimensional measures of the tumor on the baseline and follow-up MRI scans. Modified Macdonald criteria will be used [J Clin Oncol 1990; 8:1277-1280]. Responses will be defined as:

Complete response: Complete resolution of all tumor.

Partial response: \geq 50% decrease in the 2-dimensional size of the tumor.

Stable disease: < 50% decrease to < 25% increase in the 2-dimensional size of the tumor.

Progressive disease: $(1) \ge 25\%$ increase in the 2-dimensional size of the tumor, or (2) any new tumor focus, or (3) worsening neurological status that cannot be explained by any other cause associated with increase in tumor size (but < 25%).

Determination of favorable responses will be made via comparison to the baseline MRI, while determination of progressive disease will be via comparison to the nadir

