Source documentation will be available to support the computerized patient record and must be submitted with the case report forms and required study tools. Case report forms will not be considered source documentation. Variables that will be recorded include the patient's birth date, date of diagnosis, date of study entry and histologic diagnosis. The results of the pretreatment and end of therapy evaluations, including the extent of disease evaluation (history, physical examination and imaging studies), baseline laboratory values, renal and hepatic function, as defined per protocol, will be recorded. All study related treatment data and concomitant drugs will be recorded. The presence of toxicity at baseline, during and for 30 days after administration of the investigational agent will be monitored and recorded. The results of the extent of disease evaluation (history, physical examination and imaging studies) following each course of treatment will be recorded. The patient's disease status and last follow-up will be recorded. If disease progresses or recurs, the results of the repeat extent of disease evaluation will be recorded.

Research staff will be assigned at each POETIC center. Lead research personnel will be identified at each site. Their responsibilities will include maintaining file documentation of data for the clinical trial, pharmacokinetic or other biologic correlative study collection and analysis as outlined in this study, for each patient enrolled on study. They will also be responsible for maintaining a regulatory binder for each protocol. The designated research staff will also be responsible for submitting the data on a weekly basis by fax or mail to the RSA at MSKCC. Case report forms and required study tools along with supporting source documentation should be faxed or mailed to:

Pediatric Clinical Trials Office Memorial Sloan-Kettering Cancer Center [name] [contact] [contact]

The protocol will be conducted as a single research study effort and data from each participating institution will be included in the analysis of results.

[figure not shown]
The Protocol Chair will be responsible for the conduct of the study, and the monitoring of the progress and will review all case report forms from each participating institution.

Initial Protocol Submission

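### Complete and partial response are scored on tumor size alone, with no condition on systemic steroid dose, so shrinkage under new or raised steroids counts as response

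*Combined protocol and SAP*

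**What the plan says.** Section 12.0 sets the method: "we will compare the product of 2-dimensional measures of the tumor on the baseline and follow-up MRI scans". It adds that "Modified Macdonald criteria will be used", with a citation, and then writes out each category.

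- Complete response: "Complete response: Complete resolution of all tumor".
- Partial response: at least a "50% decrease in the 2-dimensional size of the tumor".
- Stable disease: a size change between the partial response and progression limits.
- Progression: at least a "25% increase in the 2-dimensional size of the tumor", or a new focus, or neurological worsening with a smaller size increase when nothing else accounts for it.

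The reference scan differs by direction: "Determination of favorable responses will be made via comparison to the baseline MRI, while determination of progressive disease will be via comparison to the nadir". Section 12.0 also requires progression to be unequivocal and lets doubtful cases stay on study until they are resolved.

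None of these definitions mentions steroids. Section 16.0 says "All study related treatment data and concomitant drugs will be recorded", but does not connect those records to the response call.

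**The concern.** A response criterion that looks only at size cannot separate shrinkage under study treatment from shrinkage under a steroid started or raised after the baseline scan. The documents do not say that systemic steroids can change the measured extent of these tumors. I take that as an assumption from general clinical knowledge.

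Two results depend on the response call. One is the response rate, a secondary endpoint (Sections 2.0 and 14.1) to be reported with 95% confidence intervals (Section 14.3.1). The other is the tumor-marker work, where Section 10.1 compares gene-expression profiles of responders with those of non-responders. The study is not randomized (Section 15.2), so no concurrent arm shares and offsets the error.

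**Working it through.** **1. Where steroids appear in the protocol**

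| Section | Context | Linked to scoring? |
|---|---|---|
| 3.4 | Prednisone within a historical chemotherapy regimen | No |
| 3.12 | Background on treating the rash | No |
| 9.3.1 | Treatment of infusion reactions | No |
| 9.4 | Topical use for skin toxicity | No |
| 12.0 | Not mentioned | No |
| 16.0 | Concomitant drugs recorded in general | No |

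No section carries steroid dose into the response call. Neurological status enters only the third progression criterion; response is size only.

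**2. Gap between baseline and the first response scan, pontine group**

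- Section 8.0 lists a pre-operative MRI for everyone and a post-operative MRI for high-grade astrocytoma only. It exempts the pre-operative MRI from the 30-day limit before registration.
- Section 6.1 allows up to 42 days from radiological diagnosis to the start of therapy.
- Section 9.1.0 puts the radiation phase at about 6½ weeks: 6.5 × 7 = 45.5 days.
- Section 10.0 puts the first tumor assessment about 3 weeks after radiation: 21 days.

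If the diagnostic scan is the baseline and was done on the day of diagnosis, the gap can reach 42 + 45.5 + 21 = 108.5 days, or about 15½ weeks. Nothing in the scoring rules deals with a steroid change over that time.

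**3. Size of the effect on the response rate**

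The plan sets no target for response, so there is no planned figure to reproduce. If k patients are scored as responders only because of steroids, the rate rises by k/n. I take n as the planned accrual, 25 and 26, assuming that all start treatment.

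| k (assumed) | Pontine, k/25 | High-grade astrocytoma, k/26 |
|---|---|---|
| 1 | 4.0 points | 3.8 points |
| 2 | 8.0 points | 7.7 points |
| 3 | 12.0 points | 11.5 points |

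The documents give no value for k.

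**4. Primary design, for reference**

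Exact binomial tails reproduce Sections 14.1.1 and 14.1.2:

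- Pontine: P(X ≥ 6 | 25, 0.10) = 0.0334 and P(X ≥ 6 | 25, 0.30) = 0.8065.
- High-grade astrocytoma: P(X ≥ 14 | 26, 0.35) = 0.0377 and P(X ≥ 14 | 26, 0.60) = 0.8007.

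Both meet the stated 5% and 80%. The response definition does not enter these figures.

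**The case against.** **The cited criteria may already contain a steroid rule.** The source is not available here, so this cannot be checked. But the protocol calls its version modified and then writes out its own definitions without such a rule. Readers at several institutions cannot tell whether a rule in the cited paper is meant to survive. The citation therefore does not close the gap, though one sentence from the sponsor could.

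**The data may already be there.** Section 16.0 records concomitant drugs, and Appendix 2, whose contents are not shown, may schedule more. This makes the fix cheap and may allow a later sensitivity review. It does not change how Section 12.0 scores a scan.

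**The mechanism and direction are uncertain.** Section 3.1 describes pontine tumors as typically enhancing little or not at all, so a route through enhancement is weak in that group. If steroids were high at baseline and lower later, the error could hide a response instead. That the baseline scan predates steroids is a possibility, not a documented fact. These points stand, and they limit the claim to what can happen.

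**Stronger readings that the documents do not support**

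- A reader might infer that steroid changes threaten the primary endpoint, since each verdict turns on one patient (5 versus 6 of 25; 13 versus 14 of 26). That is true of any cut-off. Progression must be unequivocal, biopsy is available, and the neurological criterion already excludes worsening with another explanation, which covers a steroid reduction. Only the size criterion has no reference to steroid change. Even there, a false call matters only if the patient would otherwise have been progression free at one year.
- A reader might take a hypothetical tumor area of 100 at baseline, 60 at nadir and 78 after a steroid reduction as automatic progression, because 78/60 = 1.30. The size criterion is met, but the call must still be unequivocal.
- A reader might take the opening of Section 9.4, "Clinical judgment may be used to alter the following guidelines without being a protocol violation", as freeing systemic steroids. It covers the supportive-care items listed there, and the only steroid item is topical.

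**Conclusion.** The point holds for response. As Section 12.0 is written, a halving of tumor size on newly started or raised systemic steroids is a partial response, and nothing elsewhere prevents that. Each such patient adds 4.0 points to the pontine response rate or 3.8 points to the high-grade astrocytoma rate, and moves one patient to the wrong side of the marker comparison. The number of such patients is unknown, so this is a possible upward bias, not an estimated one. It rests on the assumption that steroids can alter measured tumor size.

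For progression, the gap is limited to the size criterion and partly covered by existing safeguards. No effect on the primary endpoint is shown. Response is a secondary endpoint without a hypothesis test, and Section 14.3.2 makes the marker analyses descriptive. The change is still worth making, because it supplies a definite scoring rule at small cost.

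**What to change.** Amend Section 12.0 as follows. All three items concern scoring and reporting; none touches how steroids are used in care.

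1. Count complete or partial response only if the systemic steroid dose at that scan is no higher than at the baseline scan. Otherwise the best category is stable disease.
2. Record the daily systemic steroid dose at baseline and at each protocol MRI on the response form, and identify there which scan is the baseline.
3. As a sensitivity listing, report every size-based progression call made at a steroid dose lower than at the nadir scan. This flags the calls and does not reclassify them.

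The cost is a short amendment and one field per MRI, drawing on concomitant-drug data already collected. The reported response rate may be slightly lower. Where the dose at a diagnostic scan cannot be recovered, show those responses separately.

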13.0 CRITERIA FOR REMOVAL FROM PROTOCOL THERAPY AND OFF STUDY CRITERIA

13.1 Criteria for Removal from Protocol Therapy

- Tumor recurs or progresses
- Second malignancy
- Intolerable toxicity occurs
- Unable to start the second phase of therapy (irinotecan and cetuximab) within 56 days of completion of RT
- The patient is significantly non-compliant with the treatment plan
- The patient withdraws consent for protocol-prescribed therapy
- Completion of protocol-prescribed therapy

13.2 Off study criteria

- Death occurs
- Withdrawal of consent for any further data submission

14.0 BIOSTATISTICS

14.1 DEFINITION OF ENDPOINTS

The primary endpoint of this study is progression free survival at one year. Progression will be measured from initiation of therapy until first documented progression of disease. Death or the unlikely event of loss to follow-up, within one year will also be counted as progression. Those who are alive and progression free one year after initiation of therapy will be considered treatment successes for the evaluation of the primary endpoint.

Response is considered as a secondary endpoint. All patients who have initiated therapy will be evaluated for response. Only patients who were declared ineligible and removed prior to receiving any treatment will be excluded.

14.1.1 DIFFUSE PONTINE TUMORS

For this group of patients the goal is to effectively discriminate between progression free survival rates at one year of $\leq 10\%$ and $\geq 30\%$ using a single stage design.

The progression free proportion is deemed unacceptable if it is lower than 10% and is promising if greater than 30%. The null hypothesis that the proportion progression free at one year (p) is less than or equal to 0.10 (H0: $p \le 0.10$) will be tested against the alternative hypothesis that p is greater than or equal to 0.30 (H1: $p \ge 0.30$). For this group of tumors, we will accrue 25 patients. If 6 or more are alive and progression free at one year, the treatment will be declared effective and worthy of further testing. If 5 or fewer are alive and progression free at one year, then this group of the trial will be declared to have a negative result. This design yields $\ge 80\%$ probability of a positive result if the true percentage of patients alive and progression free at one year is $\ge 30\%$ (80% power). It yields $\ge 95\%$ probability of a negative result if the true percentage is $\le 10\%$ (5% type I error).

14.1.2 HIGH-GRADE ASTROCYTOMAS

For this group of patients the goal is to effectively discriminate between progression free survival rates at one year of $\leq 35\%$ and $\geq 60\%$, using a single stage design.

The progression free proportion is deemed unacceptable if it is lower than 35% and is promising if greater than 60%. The null hypothesis that the proportion progression free at one year (p) is less than or equal to 0.35 (H0: $p \le 0.35$) will be tested against the alternative hypothesis that p is greater than or equal to 0.60 (H1: $p \ge 0.60$). For this group of tumors, we will accrue 26 patients. If 14 or more are alive and progression free at one year, the treatment will be declared effective and worthy of further testing. If 13 or fewer are alive and progression free at one year, then this group of the trial will be declared to have a negative result. This design yields $\ge 80\%$ probability of a positive result if the true percentage of patients alive and progression free at one year is $\ge 60\%$ (80% power). It yields $\ge 95\%$ probability of a negative result if the true percentage is $\le 35\%$ (5% type I error).

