3.3 CHEMOTHERAPY HAS NOT BEEN EFFECTIVE FOR DIFFUSE INTRINSIC PONTINE TUMORS

Conventional-dose chemotherapy (usually administered in conjunction with external beam radiation therapy) has not been proved to be effective for diffuse pontine tumors. CCG 9941 was a randomized phase II trial of 2 intensive pre-radiation chemotherapy regimens for children with newly diagnosed diffuse pontine tumors [J Clin Oncol 2002, 20:3431-3437]. Thirty-two patients received regimen A: vincristine (1.5 mg/m2), carboplatin (600 mg/m2/day x 2) and etoposide (167 mg/m2/day x 3). Thirty-one received regimen B: vincristine (1.5 mg/m2), cisplatin (100 mg/m2), cyclophosphamide (1500 mg/m2/day x 2) and etoposide (167 mg/m2/day x 3). Regimen A resulted in a 10% (+/- 5%) objective response rate (\geq 25% decrease in 2-dimensional tumor size) while regimen B resulted in a 19% (+/- 8%) objective response rate. All patients then received hyperfractionated radiation therapy (7200 cGy) and 2-year event-free survival for the entire group was only 6%. These results were not considered to be superior to the historical results with radiation therapy alone. Additionally, high-dose thiotepa-based chemotherapy regimens with stem cell rescue explored by MSKCC/CCG [J Neurooncol 1998, 37:67-73] and French [Cancer 2000, 88:685-692] investigators have similarly not been effective for diffuse pontine tumors.

A variety of agents have been used in conjunction with radiation therapy, often as putative radiation sensitizers, including high-dose tamoxifen [J Clin Oncol 2000, 18:1246-1253], topotecan [Neurooncol 2003, 5:8-13], and etanidazole [Int J Radiat Oncol Biol Phys 2003, 55:1182-1185]. None has yet been demonstrated to be superior to radiation therapy alone, and there is some evidence that the combined use of external beam radiation therapy and radiosensitizers may actually be worse than radiation therapy alone. POG investigators non-randomly compared patients with diffuse pontine tumors treated with hyperfractionated radiation therapy plus concurrent cisplatin on POG 9239. A strong trend towards inferior 1-year survival amongst patients treated with combined therapy was noted [Int J Radiat Oncol Biol Phys 2000, 47:561-564].

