4.0 OVERVIEW OF STUDY DESIGN/INTERVENTION

This is a 2-group parallel (high-grade astrocytoma, diffuse pontine tumor), single stage study investigating cetuximab in conjunction with external beam radiation therapy, followed by cetuximab and irinotecan in pediatric and young adult patients. Optional exploratory components of the study include (1) correlation of tumor molecular markers with outcome, (2) CSF proteomics, and (3) assay of serum cytokine levels in patients who develop a cetuximab-associated rash.

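### No rule closes a group's accrual once its negative result is certain; closing it then would cost no error rate and would spare a few patients, mainly in the astrocytoma group if accrual is slow

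*Combined protocol and SAP*

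**What the plan says.** Section 4.0 describes the design: "This is a 2-group parallel (high-grade astrocytoma, diffuse pontine tumor), single stage study". Section 14.1 sets the endpoint and what counts against it: "The primary endpoint of this study is progression free survival at one year", and "Death or the unlikely event of loss to follow-up, within one year will also be counted as progression".

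The decision rules follow in 14.1.1 and 14.1.2.

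- **HGA:** "For this group of tumors, we will accrue 26 patients". Fourteen or more successes is positive. "If 13 or fewer are alive and progression free at one year, then this group of the trial will be declared" negative.
- **Pontine:** 25 patients, with six or more successes positive. "If 5 or fewer are alive and progression free at one year, then this group of the trial will be declared" negative.

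The only early stopping rule is the toxicity rule in 14.2, which pools both groups up to 51 patients. Section 16.1 provides a weekly steering call with biostatistical support, and 16.2 provides semi-annual review by the data and safety monitoring committee. Neither section gives an efficacy or futility criterion tied to accrual.

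**The concern.** The endpoint is asymmetric in time. A success needs a full year of follow-up, but a failure counts as soon as it is documented. A group can therefore reach the number of failures that rules out a positive result while it is still enrolling. From then on, a new patient takes on the risk of an investigational combination without being able to affect that group's efficacy conclusion, although 17.0 lists alternatives to taking part. Section 3.6 says cetuximab with radiation had not been studied in pediatric patients. The HGA null rate is also a realistic outcome: 3.4 cites recent one-year event-free survival of 31% and 36% for the two main histologies.

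**Working it through.** **Inputs from the documents.** HGA: n = 26, r = 14 successes needed, p0 = 0.35, p1 = 0.60 (14.1.2). Pontine: n = 25, r = 6, p0 = 0.10, p1 = 0.30 (14.1.1). MRI is done about 3 weeks after radiation and then in cycles 3, 6 and 9 (10.0). Progression must be unequivocal (12.0).

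**Step 1: reproduce the plan's figures.** With X binomial(n, p):

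- HGA: P(X ≥ 14 | 26, 0.35) = 0.0377; P(X ≥ 14 | 26, 0.60) = 0.8007.
- Pontine: P(X ≥ 6 | 25, 0.10) = 0.0334; P(X ≥ 6 | 25, 0.30) = 0.8065.

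Both groups meet the stated 5% and 80%.

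**Step 2: when the result is certain.** A negative result is fixed at failure number n − r + 1.

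- HGA: 26 − 14 + 1 = 13, which leaves at most 26 − 13 = 13 successes.
- Pontine: 25 − 6 + 1 = 20, which leaves at most 25 − 20 = 5 successes.

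**Step 3: effect on error rates.** The rule acts only when at least n − r + 1 failures have occurred. Every such trial ends with X ≤ r − 1 whether or not the remaining patients are enrolled. No verdict changes, so the four probabilities in Step 1 are unchanged.

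**Step 4: upper bound on the saving.** At most 26 − 13 = 13 HGA or 25 − 20 = 5 pontine patients could be spared. If every outcome were known at once, expected enrolment at p0 would be 19.9 of 26 (HGA) and 22.2 of 25 (pontine). Follow-up takes time, so the real saving is smaller.

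**Step 5: saving in calendar time.** The documents give no accrual rate, so 0.5, 1 and 2 patients per month are assumed (Poisson entry, 20,000 simulated trials per setting). Detection is either immediate or only at approximate MRI times of 2.25, 4.6, 6.7, 8.8 and 12 months. The PFS curve is exponential or Weibull with shape 2, matched to the one-year rate. Entries are mean patients spared, with the share of trials closing early in brackets where available.

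| Group, true rate | Patients per month | Immediate, exponential | At MRI, exponential | At MRI, Weibull |
|---|---|---|---|---|
| HGA, 35% | 0.5 | 3.9 (about 80%) | 3.4 | 2.6 |
| HGA, 35% | 1 | 2.2 (58%) | 1.5 (46%) | 0.8 (27%) |
| HGA, 35% | 2 | 0.4 (17%) | 0.15 (7%) | 0.02 (1%) |
| Pontine, 10% | 0.5 | 1.3 | 1.0 | 0.6 |
| Pontine, 10% | 1 | 0.5 | 0.24 | 0.06 |
| Pontine, 10% | 2 | 0.04 | about 0 | about 0 |

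Death or clinically evident progression would be seen between scans, so for a given curve the truth lies between immediate detection and detection at MRI.

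**Step 6: a second set of assumptions.** This used uniform entry over a fixed accrual period, quarterly detection, both curve shapes and 40,000 runs per setting.

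- HGA at 35%: mean spared 0.0, 0.4–1.1, 1.5–2.3 and 3.0–3.6 for accrual over 1, 2, 3 and 5 years. The chance that anyone enters after certainty is 0–1%, 18–37%, 45–61% and 71–78%.
- Pontine at 10%: mean spared 0.0, 0.0–0.1, 0.2–0.5 and 0.7–1.1.
- HGA at 60%: the rule closes accrual early in at most 6% of trials, even with 5-year accrual.

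**The case against.** The strongest reply is that a single-stage design is a declared choice that meets its stated error rates, and that no section promises an efficacy stop. That stands. The proposal leaves the choice intact, since it adds no interim test and changes no verdict.

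The second reply is that late entrants are not wasted. Section 2.0 makes the safety of cetuximab with radiation a primary objective, and the rule in 14.2 runs to all 51 patients. This also stands: a late entrant cannot change the efficacy verdict but still adds safety data, as well as response and survival data. It has to be counted as a cost.

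The third reply is that the steering call and the monitoring committee could act without a written rule. They could, but nothing gives them a number to act on.

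Three stronger readings are tempting and are not supported.

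- A reader might assume that each failure is known on the day it happens. Scans are periodic (10.0), progression must be unequivocal and may need biopsy (12.0), and loss to follow-up cannot be dated that way. Immediate detection gives only the upper end of the range.
- A reader might cite 3.3, where "there is some evidence that the combined use of external beam radiation therapy and radiosensitizers may actually be worse than radiation therapy alone", as grounds for futility monitoring of HGA. That section is about pontine tumors, and its example is a non-randomized comparison involving cisplatin. Section 3.6 also cites an adult head and neck trial in which adding cetuximab to radiation improved outcomes.
- A reader might infer that both groups would enrol many patients after certainty. The pontine saving is about one patient or fewer, and either saving nearly vanishes if a group fills in about a year.

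**Conclusion.** The plan lacks a rule to close a group whose negative result is already certain. This is an inexpensive missing safeguard; it is not a calculation error or a flaw in the single-stage design. The benefit lies mainly in the HGA group under slow accrual: about 3 to 4 patients on average at 0.5 per month, about 1 to 2 at 1 per month, and almost none at 2 per month, if the true one-year rate is 35%. It would be larger below that rate. These sizes rest on assumed accrual rates, detection times and PFS shapes. The certainty points (13th and 20th failure) and the unchanged error rates rest on none of these.

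**What to change.** Add to 14.1.1 and 14.1.2: *Accrual to the pontine group closes at the 20th, and to the HGA group at the 13th, documented one-year failure as defined in 14.1, since the negative result is then certain. Enrolled patients continue to be followed, and the running count is reviewed at the weekly steering call.* Name who keeps the count.

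Add to 14.2 that if a group closes this way, the pooled toxicity rule runs on slightly fewer than 51 patients, so its tabulated completion probabilities no longer apply exactly.

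The cost is a running tally and a few fewer patients for the safety objective and for the response and survival estimates of a negative group. Type I error and power are unaffected. If the sponsor prefers full accrual for safety or the secondary aims, the plan should say so and give that reason.
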